8.1.2 Subsequent Prostate Cancer Treatment

8.1.2.1 Proportion of Subjects with Subsequent Prostate Cancer Treatment

Types of systemic and non-systemic prostate cancer therapies are recorded in the Treatment Type field of the Systemic Prostate Cancer Therapy and Non-Systemic Prostate Cancer Therapy CRFs, respectively. Subjects may indicate more than one treatment type. Treatment types will be categorized into groups as follows:

- Surgery
 - Radical Prostatectomy
 - Orchiectomy
 - Cryotherapy or Cryosurgery
- Radiation
 - External Beam Radiation Therapy (EBRT)
 - Brachytherapy
- Androgen Deprivation Therapy (ADT)
 - GnRH agonist

- GnRH antagonist
- Enzalutamide
- Apalutamide
- Darolutamide (ODM-201)
- Bicalutamide
- Abiraterone Acetate (Zytiga)
- Abiraterone Acetate (Yonsa)
- High Intensity Focused Ultrasound (HIFU)
- Vascular Targeted Photodynamic Therapy

“Other” treatment type will be specified in the free text field “Other Specify” and will be reviewed for appropriate classification into one of the groups above. The rules of classification for “Other” treatment types will be outlined in the ADaM Reviewer’s Guide.

The proportion of subjects with prostate cancer treatment in each category will be calculated for analysis.

8.1.2.2 Time to the First Subsequent Prostate Cancer Treatment

The first prostate cancer treatment is the treatment with the earliest start date on the Systemic Prostate Cancer Therapy or Non-Systemic Prostate Cancer Therapy CRF. The time to first prostate cancer therapy (weeks) is defined as (earliest start date of all prostate cancer therapies – date of randomization + 1)/7. Censoring rules applied to time to prostate cancer therapy are:

- If start date for any treatment is missing, then censor event time at randomization date
- If no post-randomization assessment for prostate cancer treatments, then censor event time at randomization date
- If no subsequent prostate cancer treatment, then censor event time at the date of the last assessment for prostate cancer treatments

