(H&E) and special-stained slides from this biopsy will be submitted for BICR determination of their ISUP Grade Group classification prior to study withdrawal. All AEs considered by the investigator to be related to sipuleucel-T that are ongoing at the time of discontinuation will be followed by the investigator until resolution, return to baseline, or a determination by the investigator that no further improvement is expected. The investigator should make every reasonable attempt to ensure that the subject is contacted (via telephone or during the Early Withdrawal Visit) to obtain the final status of any AEs and concomitant medications.

After Screening assessments are completed, eligible subjects will be randomized 2:1 to the sipuleucel-T arm or the control arm, respectively. Subjects randomized to sipuleucel-T arm will undergo their first leukapheresis within 60 days of randomization and will receive 3 infusions of sipuleucel-T at approximately 2-week intervals. Subjects randomized to the control arm will be followed on AS as described in the schedule of events (Table 2 of the protocol).

Subjects randomized to the sipuleucel-T arm will be evaluated at 0, 2, 4, 6, 10, 14, and 26 weeks following the first infusion for:

- Immune responses (Week 0 prior to first infusion is baseline)
- All anti-prostate cancer therapies
- Concomitant medications
- AEs and serious adverse events (SAEs) (per reporting requirements for the sipuleucel-T arm)

Subjects randomized to the control arm will be evaluated (office visit or phone) at 3 months following randomization for:

- Survival status
- All anti-prostate cancer therapies
- Concomitant medications
- All AEs and SAEs

Subsequently, all subjects in the sipuleucel-T and control arms will be followed every 6 months from date of randomization for at least 36 months for:

- Immune responses (sipuleucel-T arm only)
- Survival status
- PSA levels (should be collected prior to DRE and biopsy procedures)
- DRE assessments
- Prostate cancer disease progression
- All anti-prostate cancer therapies
- Concomitant medications
- All AEs and SAEs

Note, for subjects randomized to the sipuleucel-T arm, scheduled events for the 26-week visit post first infusion and first 6-month visit post-randomization may take place on the same visit and only one set of immune samples need to be collected.

During the Active Phase, all subjects in the sipuleucel-T and control arms will complete:

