12.6.2 Secondary Endpoints

12.6.2.1 Subsequent Prostate Cancer Treatment

The counts and proportions of subjects receiving subsequent prostate cancer treatment will be presented overall and by each type of cancer treatment and reason for therapy in both study treatment arms of the ITT and PP analysis sets. The exact 95% confidence intervals for the proportions will be presented as well.

Time to first subsequent prostate cancer treatment will be summarized using Kaplan-Meier (KM; [Kaplan and Meier 1958](#)) estimates for the ITT and PP analysis sets. The 25%, 50%, and 75% quartiles will be calculated and corresponding 95% CIs by the KM method. A KM plot for time to first subsequent prostate cancer treatment will be presented. The count and proportion of responding subjects who have an event or are censored will be summarized.

Subsequent prostate cancer treatment data will be provided in a listing.

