12.7.5 Methods for Handling Dropouts and Missing Data

Below are rules for imputing missing or partial dates for analyses of medical history, AEs, and concomitant medications. Though imputed for analyses, actual dates (missing or partial) will be reflected in listings. Otherwise, there will be no imputation of missing data values. Data on subjects who withdraw early will be summarized up until the time of withdrawal.

Missing or partial dates for medical history will be imputed as follows:

- If only the day is missing, it will be imputed with the 15th day of the month.
- If both the day and month are missing, the month and day will be imputed with July 1st.
- If the date is completely missing, no imputation will be performed.

Missing or partial dates for AEs and concomitant medications will be imputed as follows:

- Start Date
 - If only the day is missing and the month and year are the same as the month and year of the first dose date, then the day will be imputed with the day of the first dose date. Otherwise the day will be imputed with the first day of the event month.
 - If both the day and month are missing and the year is the same as the year of the first dose date, then they will be imputed with the month and day of the first dose date. Otherwise they will be imputed with the July 1st of event year.

- If the start date is completely missing, the date will be imputed with the first dose date.

If the stop date is complete and the imputed start date is after the stop date, then the imputed start date will be set to the stop date.

- Stop Date
 - If only the day is missing and the month and year are the same as the month and year of the study discontinuation date, then the day will be imputed with the day of the study discontinuation date. Otherwise the day will be imputed with the last day of the event month.
 - If both the day and month are missing and the year is the same as the year of the study discontinuation then they will be imputed with the month and day of the study discontinuation date. Otherwise they will be imputed with the December 31st.
 - If the stop date is completely missing, then it will be imputed with the study discontinuation date.

Note that stop date imputation will not be applied to ongoing AEs. If the imputed stop date is greater than last the contact date, then the imputed stop date will be set to last contact date.

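### SAP 8.1.2.2 censors a man known to have been treated at randomization when a treatment start date is missing, so the Kaplan-Meier analysis of time to first treatment understates treatment use

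*SAP*

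**What the plan says.** SAP 8.1.2.2 defines the event by date: "The first prostate cancer treatment is the treatment with the earliest start date" on either of the two prostate cancer therapy forms. Three censoring rules follow.

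- The first concerns missing dates: "If start date for any treatment is missing, then censor event time at randomization date".
- The second censors at randomization a man who was never assessed for treatment after randomization.
- The third covers untreated men: "If no subsequent prostate cancer treatment, then censor event time at the date of the last assessment for prostate cancer treatments".

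SAP 12.6.2.1 then applies the variable: "Time to first subsequent prostate cancer treatment will be summarized using Kaplan-Meier" estimates, in the ITT and PP sets, with quartiles and their confidence intervals, a plot, and counts of events and censored men. No between-arm test is stated for it.

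The companion analysis in SAP 8.1.2.1 uses no start date: "The proportion of subjects with prostate cancer treatment in each category will be calculated for analysis".

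The SAP's date imputation is in 12.7.5, within the safety analyses, and has a stated scope: "Below are rules for imputing missing or partial dates for analyses of medical history, AEs, and concomitant medications". It adds: "Otherwise, there will be no imputation of missing data values". Prostate cancer therapies have their own forms and are not named there. The SAP does not say whether a partial date counts as missing under 8.1.2.2.

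**The concern.** A start date can be missing only if a treatment has been recorded. Former prostate cancer therapy is an exclusion (Protocol 6.2.1), so for an eligible man the record means that treatment began on study. The event is certain and only its time is unknown. The rule nevertheless gives him the same status as a man who was never assessed.

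Kaplan-Meier estimation needs censoring that carries no information about the event. Here the rule applies only to men who had the event, so that condition fails by construction and the bias has one direction: too little treatment.

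The wording also reaches further than a man with no usable date. It is triggered by a missing date for *any* treatment. Taken literally, a man with a dated prostatectomy and a later undated therapy is censored at randomization, although the definition in the same section gives him an event on the prostatectomy date. SAP 8.1.2.1 expects that some men will have more than one treatment type.

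At stake is one of the two measures that SAP 7.2.1 lists for subsequent treatment, which serves the secondary objective on differential receipt of therapy. Any affected man will be treated in the proportion table and censored in the Kaplan-Meier output.

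**Working it through.** **No plan figure to reproduce.** The documents give no event rate, event number, power or missing-date rate for this endpoint. The sample-size figures in SAP 6.2 concern the primary endpoint and have no bearing here. The treated and undated shares below are assumptions.

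**Formula.** Let N men be randomized to an arm, D of them treated by 36 months, and k of those D have a missing start date. Assume that everyone else is followed to 36 months. The true treated proportion is D/N. Under the rule the k men contribute no event and essentially no time at risk, so the Kaplan-Meier estimate is

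(D − k)/(N − k).

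With p = D/N and m = k/D this is p(1 − m)/(1 − pm).

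**Results.**

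| Undated share of treated men, m | p = 20% | p = 30% |
|---|---|---|
| 1% | 0.198/0.998 = 19.8% | 0.297/0.997 = 29.8% |
| 5% | 0.190/0.990 = 19.2% | 0.285/0.985 = 28.9% |
| 10% | 0.180/0.980 = 18.4% | 0.270/0.970 = 27.8% |
| 20% | 0.160/0.960 = 16.7% | 0.240/0.940 = 25.5% |

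The shortfall runs from about 0.2 points (20.0 − 19.8) to 4.5 points (30.0 − 25.5). A product-limit calculation on simulated arms agrees with the closed form. For example, with N = 300, D = 60 and k = 6, both give 54/294 = 18.4%.

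**Effect on an output the SAP names.** SAP 12.6.2.1 asks for quartiles rather than a 36-month proportion. With 20% treated by 36 months, none is reached by then. With 30% treated and starts spread evenly over 36 months (a further assumption), the true first quartile is 36 × 0.25/0.30 = 30.0 months. Under the rule it becomes 36 × 0.25/0.289 = 31.1 months at 5% undated, 36 × 0.25/0.278 = 32.4 at 10%, and 36 × 0.25/0.255 = 35.3 at 20%.

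**Does another provision rescue the event?** SAP 12.7.5 does not name these therapies. The sensitivity analyses in SAP 12.6.1.3 do not address this rule. The contrast within the SAP is plain: an adverse event with a completely missing start date is given an imputed date and kept, while a known cancer treatment is dropped as an event.

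**The case against.** **No decision rests on this curve.** The SAP summarizes it without a test, and SAP 12.6.1.2 says that the single primary test decides the study. The between-arm comparison of subsequent treatment in Protocol 10.5.2 is a Cochran-Mantel-Haenszel test, which needs no start date. This stands, and it limits the severity.

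**The men remain visible.** The proportion table counts them and SAP 12.6.2.1 provides a listing. A reader might infer that treated men vanish from the report; they do not. But the listing does not correct the curve, quartiles or event count.

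**Missing dates may be rare.** Treatment is asked about at repeated visits, receiving it ends the Active Phase, sites are monitored (Protocol 11.4), and data issues are queried before lock (SAP 11.0). That is fair, and it is why the range starts at 1%. At 5% undated with 20% treated, the 0.8-point bias is small beside a 95% half-width of 1.96 × √(0.2 × 0.8/300) = 4.5 points, or 6.4 points with 150 men.

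**The sponsor may have meant that no usable date exists.** This is plausible, given the definition in the same section. The loss of a dated first treatment is therefore a literal reading that needs resolving, not an established intention. Even on the narrower reading, a man with no date at all is still censored at randomization despite a known event.

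**A stronger reading: a false difference between arms.** It would follow if missingness differed. With 20% treated in both arms and 10% undated in control only, the estimates are 60/300 = 20.0% and 27/147 = 18.4%. The documents give no reason to expect this. The visit schedules differ only early, and then both arms are "followed every 6 months from date of randomization for at least 36 months".

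**Conclusion.** The rule is wrong as written. It makes censoring depend on the outcome, biases the Kaplan-Meier curve and event count downward in any arm with an affected man, and, on its literal wording, contradicts the section's own definition of first treatment. The error does not depend on how often dates are missing; its size does. With 20% to 30% treated, no other censoring and 1% to 20% of treated men undated, the shortfall is about 0.2 to 4.5 percentage points. Neither the treated share nor the undated share comes from the documents, and if every date is recorded the rule does nothing.

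The consequence is confined to a descriptive secondary analysis. The primary analysis does not use this variable, and the proportion treated needs no start date. The documents do not support a claim that the rule favors one arm. The correction should be made before database lock, but it does not threaten the trial's main conclusion.

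**What to change.** Replace the first censoring rule in SAP 8.1.2.2 so that a man with any recorded post-randomization prostate cancer treatment counts as an event, timed as follows.

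1. If at least one start date is known, use the earliest. Where an undated therapy could have come before it, treat that date as the latest possible event time.
2. If a date is partial, impute it by a stated rule, bounded by randomization and last contact, and say that a partial date is not a missing one.
3. If no date is known, place the event between the last assessment recording no treatment and the first recording treatment, for example at the midpoint. With 6-monthly visits and none missed, the midpoint is off by at most about 6/2 = 3 months, apart from visit windows.

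Add a sensitivity analysis that sets each uncertain event to its earliest and then its latest possible date, and report the number of men affected by arm. The midpoint is one reasonable choice; interval-censored estimation is another.

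The cost is a few lines of SAP text and code, with no new data collection. The downside is slight imprecision in a few imputed event times, which the sensitivity analysis makes visible.

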8.1.3 Patient Reported Outcomes (PROs)

The following PROs are reported at baseline and at every 12-month visit. For each of the scores defined below, the change from baseline at each timepoint and maximum change (toward favorable outcome) during any assessment within 36-month after randomization, including unscheduled visit, minus the baseline score.

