6.7 Restricted Therapies During Sipuleucel-T Treatment Period

Certain therapies and procedures could confound the results of this study. Therefore, subjects who are randomized to the sipuleucel-T arm and receive any of the following, 30 days prior to the first infusion until 30 days after the last infusion, will discontinue sipuleucel-T treatment (Section 6.3.1):

- Any immunosuppressive therapy, including systemic steroids. Use of inhaled, intra-nasal, intra-articular, and topical steroids is allowed. Oral or IV steroids to prevent or treat IV contrast reactions are allowed
- Blood products
- GM-CSF or G-CSF
- Any vaccinations

Subjects that discontinue sipuleucel-T treatment and have received > 0 mL of sipuleucel-T will remain in the Active Phase and follow the schedule of events (Table 1).

6.8 Restricted Therapies from Randomization to End of Active Phase (Sipuleucel-T and Control Arms)

Certain therapies and procedures could confound the results of this study. Therefore, subjects who receive any of the following will go from Active Phase of the study to the Follow-up Phase of the study:

- Any local or systemic therapy or procedures for prostate cancer (e.g., ADT, radical prostatectomy, external beam radiation or brachytherapy)
- Any local or systemic therapy or procedure targeting the prostate (e.g., transurethral resection of the prostate (TURP) or 5-alpha reductase inhibitor)
- Major surgery at the discretion of the sponsor's Medical Monitor
- Any investigational product for prostate cancer or other condition (per sponsor's Medical Monitor approval)
- Any other therapy at the discretion of the sponsor's Medical Monitor

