8.7 Patient Reported Outcomes

PRO data will be collected to evaluate health-related quality of life for men on AS and the impact of any subsequent therapy for prostate cancer. Four instruments SF-12 ([Appendix 2](#)), MAX-PC ([Appendix 3](#)), EPIC-CP ([Appendix 4](#)), and the IPSS ([Appendix 5](#)) will be administered at Screening, annually during the Active Phase at 12-, 24-, and 36-month visits, and every 6 months in the Follow up Phase or Early Withdrawal Visit. SF-12 evaluates the general quality of life, MAX-PC evaluates a subject's anxiety related to prostate cancer diagnosis, EPIC-CP measures quality of life issues in patients with prostate cancer, and the IPSS evaluates patient's urinary voiding symptoms. PROs should be administered prior to any procedures or measurements. The clinical site staff must review the completed PRO's with the subject prior to leaving the facility to ensure that PROs have been completed correctly.

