10.5.2 Secondary Endpoints

The subsequent prostate cancer treatment, if any, for each subject will be determined. The category of subsequent prostate cancer treatment will be identified (e.g., surgery, radiation, androgen deprivation therapy). Subjects initiating alternative intervention will be regarded as sipuleucel-T treatment failures. These data will be summarized descriptively and compared between study arms using the Cochran-Mantel-Haenszel test.

Quality of life data will be summarized descriptively and compared between study treatment arms and in the aggregate within the efficacy population.

Safety data will be summarized descriptively by study treatment arms and in the aggregate within the safety population.

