5.2 Secondary Objectives

- To assess the differential receipt of local or systemic therapy (surgery, radiation, androgen deprivation therapy (ADT)) in each study arm, and the reasons for receipt of further local or systemic therapy
- To assess differences in quality of life (i.e., patient-reported outcomes (PROs)) between sipuleucel-T and control arms
- To evaluate the safety of sipuleucel-T in men with low to intermediate risk localized prostate cancer

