12.6.2.2 PROs

For each PRO total score and pooled domain score or sub-score defined in [Section 8.1.3](#), actual values at baseline and change from baseline at 12, 24, and 36 months visits post randomization will be summarized in the ITT and PP analysis sets in each treatment arm. The best change within 36 months post-baseline will be summarized and compared between the arms. The responses to individual question items will not be summarized except for the EPIC-CP overall urinary function question, which will be presented at baseline and its shift change presented at post-randomization.

To assess potential missing individual items in each PRO questionnaire, a sensitivity analysis in the ITT analysis set will be conducted to calculate total scores and pooled domain scores by summing up all available individual items regardless of any missing individual score.

PRO results will be provided in a listing.

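### The only between-arm quality-of-life comparison the SAP specifies is on best change, which depends on how often a man is assessed and dilutes deterioration that is not present at every visit

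*SAP*

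**What the plan says.** The secondary objective in SAP 5.2 is "To assess differences in quality of life (i.e., patient-reported outcomes (PROs)) between sipuleucel-T and control arms".

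SAP 8.1.3 defines two quantities for each score: change from baseline at each timepoint, and the "maximum change (toward favorable outcome) during any assessment within 36-month after randomization, including unscheduled visit". SAP 12.6.2.2 treats them differently:

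- By-visit change: "change from baseline at 12, 24, and 36 months visits post randomization will be summarized in the ITT and PP analysis sets", with no comparison mentioned.
- Best change: "The best change within 36 months post-baseline will be summarized and compared between the arms". No test, model or adjustment for number of assessments is given.

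Protocol 10.5.2 says "Quality of life data will be summarized descriptively and compared between study treatment arms" but names no score, visit or method.

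On frequency, Protocol 8.7 has the questionnaires completed at Screening and then "annually during the Active Phase at 12-, 24-, and 36-month visits, and every 6 months in the Follow up Phase or Early Withdrawal Visit". Under Protocol 6.8, "subjects who receive any of the following will go from Active Phase of the study to the Follow-up Phase of the study"; the list includes any local or systemic prostate cancer therapy.

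**The concern.** The maximum of several noisy readings has two properties that make it a poor statistic for comparing arms.

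1. It depends on how many readings there are. Here that number can depend on what happens after randomization, because starting prostate therapy changes the questionnaire schedule.
2. It discards every reading except the best. A man who worsens after surgery or radiation can be represented by his score from before it. Yet Protocol 8.7 gives the impact of subsequent therapy as one reason for collecting these data.

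At stake is the interpretation of a secondary objective in an open-label trial. The one between-arm result the SAP commits to could understate a real loss of quality of life in either arm.

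**Working it through.** **Inputs from the documents.** 300 and 150 men (SAP 6.2); scheduled assessments at 12, 24 and 36 months; 6-monthly assessments in the Follow-up Phase; planned upgrading of 0.16 and 0.30 (SAP 6.2). The documents give no effect size, SD or power for any patient-reported score, so there is no planned figure to reproduce.

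**Assumptions not in the documents.** Normal scores with unit SD, equal correlation ρ between any two visits (0.5 unless stated), complete data.

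**1. Best change when nothing changes.** For k assessments, E[best change] = √(1−ρ) × E[max of k standard normals].

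| k | E[max] | ρ = 0.5 | ρ = 0.7 | ρ = 0.8 |
|---|---|---|---|---|
| 3 | 0.846 | 0.60 | 0.46 | 0.38 |
| 4 | 1.029 | 0.73 | 0.56 | 0.46 |
| 5 | 1.163 | 0.82 | 0.64 | 0.52 |

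This offset occurs in both arms. With three assessments in each, the simulated between-arm difference is 0.00 and the error is 2.4% to 2.8% in each tail, so about 5% two-sided.

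**2. How many assessments can a man have by month 36?** Count Follow-up visits every 6 months from the time he leaves the Active Phase.

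| Leaves at month | Assessed at months | Count |
|---|---|---|
| stays in Active Phase | 12, 24, 36 | 3 |
| 12 | 12, 18, 24, 30, 36 | 5 |
| 15 | 12, 21, 27, 33 | 4 |
| 20 | 12, 26, 32 | 3 |
| 31 | 12, 24 (next at 37) | 2 |

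The change can be up or down. For transfers between about months 13 and 18, around or after Biopsy 1, it is usually one extra.

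**3. Size of the resulting bias.** No document gives the proportion of men who will start therapy. As an illustration only, let 16% of sipuleucel-T and 30% of control men have extra assessments. The SD of best change is about 0.88, so SE ≈ 0.88 × √(1/300 + 1/150) = 0.088.

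- One extra: difference = (0.16 − 0.30) × (0.728 − 0.598) = −0.018 SD. Two-sided error ≈ 5.5%.
- Two extra: difference = (0.16 − 0.30) × (0.822 − 0.598) = −0.031 SD. Two-sided error ≈ 6.5%.

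Simulations of the same cases gave 5.8% for one extra and 6.2% to 6.8% for two. In this illustration the bias favours control.

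**4. Dilution of harm.** Three assessments in each arm, sipuleucel-T worse by 0.5 SD at some visits:

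| Visits affected | Loss in best change, ρ = 0.5 | ρ = 0.8 |
|---|---|---|
| one | 0.12 | 0.10 |
| two | 0.28 | 0.25 |
| three | 0.50 | 0.50 |

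**5. Chance of detecting a 0.3 SD harm** (two-sided 5%, in the direction of harm, ρ = 0.5, simulated):

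| Harm present at | Month-36 comparison | Best-change comparison |
|---|---|---|
| month 36 only | 85% | 15% |
| months 24 and 36 | 85% | 55% |
| all three visits | 85% | 92% |

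**The case against.** Several points on the other side stand.

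- A reader might infer that the comparison shows a spurious benefit of sipuleucel-T because best change is positive under pure noise. It does not: the offset is the same in both arms when assessment counts are equal, and the test keeps its level.
- A reader might also infer serious error inflation from the 6-monthly schedule. That would need a large imbalance in therapy and two extra assessments for most treated men. The documents support neither, and step 2 shows that two extra arises only for certain transfer times. Where controls have more assessments, the bias works against sipuleucel-T, so under the one-tailed superiority test in SAP 12.0 a false claim of benefit becomes rarer.
- Deterioration would not be invisible. By-visit change is tabulated by arm in both the ITT and PP sets, and harm of equal size at every visit is fully reflected in best change.
- The protocol's general sentence on comparing quality of life is not limited to best change, so calling this the only comparison is accurate for the SAP, not for the two documents together.
- These are secondary endpoints, and study success rests on the single primary test (SAP 12.6.1.2).

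What remains is that the SAP, which is meant to supply the detail, commits to a between-arm comparison of one quantity, and that quantity responds weakly to harm at some visits only. Descriptive tables by arm give no estimate of the difference with its uncertainty.

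**Conclusion.** The point holds in a limited form. The main defect is dilution: with three assessments, a 0.5 SD harm at one visit shows as about 0.12 SD and at two visits as about 0.28 SD, and these figures change little between ρ = 0.5 and 0.8. Dependence on assessment count is a second and probably small defect. Its direction cannot be known from the documents, and two-sided error is about 5% to 7% in the borrowed-rates illustration. All figures rest on normal scores, equal correlation between visits and complete data, and those for count also assume that Follow-up Phase questionnaires within 36 months enter the maximum, as the wording of SAP 8.1.3 implies. The documents do not support a claim that the test is invalid with equal schedules, that it favours sipuleucel-T, or that all deterioration is concealed. The change should be made because a by-visit comparison answers the stated objective with data already collected.

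**What to change.** In SAP 12.6.2.2, make the between-arm comparison a mixed model for repeated measures on change from baseline at 12, 24 and 36 months, with arm, visit, arm-by-visit interaction, baseline score and the randomization strata. Report the difference and two-sided 95% CI at each visit, so that harm and benefit are both readable. Keep best change as a descriptive summary only.

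Two rules must accompany the model:

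- **Analysis windows** that map Follow-up Phase, unscheduled and Early Withdrawal assessments to the three visits, with a rule for ties. A man who transfers at month 15 is assessed at 21 and 27 months, both 3 months from month 24, and next at 33. The month-36 window should say how far past month 36 it reaches; a man who transfers at month 31 is next assessed at 37.
- **Assessments after subsequent therapy are included** (a treatment-policy approach), in keeping with the stated reason for collecting them.

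The cost is SAP wording, the windowing rule and some extra programming. No new data, visits or sample size are needed. The model relies on a missing-at-random assumption, which should be stated.
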